## **Selection Criteria**

### **Inclusion:**

- Upper Extremity hemiparesis from Cerebral Palsy
- Age 6-17
- Caregiver can transport participant to weekly sessions and assist with home treatment
- Medically stable; stable medications
- Recall 2 of 3 items after 30 min
- Finger extension strength  $\leq$  4/5 on paretic side
- Able to follow 3-stage commands
- Adequate active movement of paretic arm to position the hand for table-top task practice
- Skin intact on hemiparetic arm
- Surface NMES trial opens hand without pain
- Full volitional hand opening and closing of contralateral hand
- Box & Blocks Score of weaker side  $<$  90% of stronger side score
- Able to hear and respond to auditory cues
- English proficiency of both caregiver and child

### **Exclusion:**

- Uncontrolled seizure disorder
- Co-existing neurological conditions other than CP affecting the hemiparetic upper limb (e.g., peripheral nerve injury, PD, SCI, TBI, MS, stroke, hemispherectomy)
- Severely impaired cognition and communication
- History of cardiac arrhythmias with hemodynamic instability
- Insensate arm, forearm, or hand
- Uncompensated hemi-neglect
- Cardiac pacemaker or any other implanted electronic systems
- Pregnant
- IM Botox injections in any UE muscle in the last 3 months
- Severe visual impairment

## **Informed Consent**

The participants will be under the age of 18, so proper assent will be completed along with permission from their parent(s).

The consent/assent interview will be completed in a private room at the Cleveland Clinic Children's Hospital for Rehabilitation or satellites at Westlake, Beachwood, Cuyahoga Falls, Brunswick, and Middleburg Heights. The consenting/assenting interview will be completed at least 24 hours following receipt of the consent document to allow for the participant and family to read over and ask any questions they may have. The consenting/assenting process will be documented in the participant's medical record. All participants will be current patients at Cleveland Clinic.

## **Potential Risks**

### **Device Risks**

These risks are described as common (which means it might happen greater than 10% of the time), uncommon (which means it might happen about 2-10% of the time), or rare (which means it might happen about less than 1% of the time).

*Fatigue or Pain (Common):* There is a possibility that the concentration and repetition associated with activities during lab sessions may cause "mental fatigue" from the intensity of concentration required during these tasks, or physical fatigue or pain (joint soreness, muscle

ache, or shoulder pain) due to the repetitive tasks. This will vary from person to person. This is similar to what might be experienced after working hard in a traditional occupational therapy session. If the participant experiences such pain or discomfort, we will stop treatments until the pain subsides and adjust the intensity of the treatments to prevent recurring discomfort.

*Motion Sickness (Common):* There is a possibility that the video games can cause motion sickness. Some of the video games feature objects that rotate or move in a way that may cause temporary dizziness or light headedness. We minimized the possibility for motion sickness by making the video animations smooth and by closely matching participant's hand movements with what they control in the video game. We have also designed several games, some of which feature less video movement and lower risk for causing motion sickness. However, if the participant experiences these sensations while playing a video game, we instruct them to stop playing and close their eyes or look away from the video screen. The nausea may go away with rest. If the nausea does not go away after resting or returns after playing the game again, we instruct them to discontinue playing and notify research staff. If a particular game is causing the motion sickness, we will avoid prescribing it to the participant and have them use only the games that do not cause them motion sickness.

*Uncomfortable Sensation (Common):* Electrical stimulation of a muscle may be perceived as a twitching or vibrating sensation, and may be uncomfortable. Electrical stimulation of a nerve may be perceived as a strong but short shock, and may be uncomfortable. Electrical stimulation of the skin may be perceived as a "pins and needles" sensation and may be uncomfortable. Discomfort associated with electrical stimulation is common, occurring in approximately 40% of subjects if the stimulus parameters are not well-adjusted. Stimulus parameters will be adjusted to your comfort.

*Surface Electrode/Adhesive Skin Irritation (Uncommon):* There is a chance participants may experience a temporary redness of the skin from the electrodes, the conductive gel used with them, or the adhesive used to secure them. Irritation from the electrodes occurs in approximately 10% of subjects. The irritation and redness will go away when the electrodes are removed. Skin irritation from electrical stimulation is rare, but possible. The type of stimulation that will be used minimizes the possibility.

*Electrical Hazards (Rare):* There is a rare possibility of an electrical shock hazard whenever electrical stimulation is used or whenever computers and electrical equipment are used to make measurements. There is a rare possibility of an electrical burn whenever electrical stimulation with surface electrodes is used. Electrical burns will be assessed and treated by the study physician if necessary. Electrical shocks will be assessed and treated by the study physician if necessary, and the equipment will be tested for faults. The equipment to be used has been designed and tested to minimize these risks. Participants will be trained how to use your stimulator safely and will be asked to follow to a list of safety precautions.

*Stimulator Malfunction (Rare):* There is a rare possibility that the stimulator may malfunction and produce painful stimulation even after it has been properly programmed in the laboratory. The sensation may be a sudden burning sensation, which can damage the skin if it does not stop. If participants experience pain from the stimulation, they are instructed to turn off the stimulator, discontinue its use, and contact study personnel.

## **Risk Mitigation**

All study participants and their caregivers, if applicable, are taught by a therapist how to use the stimulator at home. Pictures of the electrodes in their proper positions are given to the participants, and a manual on how to use the stimulator is reviewed with each participant and caregiver. Before a participant goes home with a stimulator, they are required to demonstrate that they can put on the device, operate it according to the given instructions, and take off the device. Participants are encouraged to call the therapist if they have any questions about using the device while at home. The following safety precautions are listed in the manual:

- Avoid handling the electrodes while the stimulator is on. Always remember to turn off the stimulator before you remove the electrodes.
- Always wash and dry the skin before applying the electrodes. Generally any mild soap is fine; avoid deodorant or perfumed soaps or lotions, as these affect skin adherence.
- Use new electrodes if the reused ones no longer stick to the skin.
- Place electrodes on the skin only where instructed.
- Never position electrodes on the chest, across the heart, or on the neck.
- Do not place electrodes over broken skin as this may cause pain and skin irritation.
- Do not submerge the stimulator in water, or use around water (spills, bathtub/shower or sink).
- Do not operate dangerous machinery or drive while using the stimulator.
- Do not sleep while using the stimulator. Remain attentive during use to avoid skin burns.
- A slight reddening of the skin under the electrode is normal. This should fade after 1 hour once the electrodes are removed. If you note redness or blistering beyond this, discontinue use and inform study personnel.
- The safety of electrical stimulation in pregnancy has not been determined; therefore, we do not enroll pregnant women.
- Electrical stimulation should not be used by patients with implanted electronic devices (cardiac demand pacemakers etc.) unless under specialized medical supervision.
- Do not participate in this study if you have a history of potentially fatal cardiac arrhythmias.
- Electrical stimulation should not be used by people who have poorly controlled epilepsy.
- The stimulator has been programmed specifically for the intended user only. Do not allow anyone else to use the stimulator.

## **STATISTICAL ANALYSIS**

### **Sample size determination**

This is a pilot randomized control trial that aims to estimate the intervention effect necessary to power a larger trial. The sample size target of 20 participants was limited by the amount of funds provided by the R21 funding mechanism.

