## **STUDY PROTOCOL**

### **1. Brief Summary of the Proposed Research**

This is a pilot randomized controlled trial of an intervention to improve arm function in children ages 6 to 17 with cerebral palsy and upper limb hemiparesis. Twenty participants will be randomized to either a group treated with neuromuscular electrical stimulation and video games or video games alone. Both groups will receive 6 wks of treatment. Changes in upper extremity motor impairment and function will be assessed for each participant at baseline, mid treatment, end of treatment and at 3 mo follow-up.

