### Specific Aims

The primary aim of this study is to collect pilot data to estimate the efficacy of CCFES videogame therapy in improving outcomes of upper extremity impairment and function. CCFES + videogame therapy is new, so estimating its effect is a first step to test our hypothesis that it leads to greater outcomes than video game therapy alone. We will assess clinical measures of upper extremity impairment, function, and community use to test this hypothesis.

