### Methods and Procedures

Both the experiment group and control group interventions last 6 weeks and consists of therapist-guided sessions in the rehabilitation clinic and self-administered or caregiver-assisted sessions at home. While both groups will receive the same task practice and video game training, only the experiment group will receive an electrical stimulation device to assist with hand opening during practice. An adaptive randomization algorithm will be used to balance the two groups with respect to age, gender, and baseline severity (not severe if the child is Manual Activity Classification System level I-II, severe if level III-V). The treatment dose will be the same for both groups: 10 sessions per wk of self-administered video game training at home plus 2 lab sessions per wk for the first 3 wks and 1 lab session per wk for the final 3 wks – 58 hrs total. Blinded assessment of upper limb impairment and function will be done at baseline, mid-treatment, end-of-treatment, and 3-mos post-treatment.

- Note: Contralaterally controlled electrical stimulation (CCFES) – Enables patients with upper extremity hemiplegia to open their paretic hand by stimulating finger and thumb extensors with surface electrodes. Stimulation is proportional to degree of unimpaired hand opening as detected by an instrumented glove worn on the unaffected hand. Thus, volitional opening of the non-paretic hand produces stimulated opening of the paretic hand. CCFES is used during functional task practice and hand therapy video games to link motor intent with execution.
- Note: Hand Therapy Video Games – Four intuitive and engaging games were developed specifically for play with CCFES to provide goal-oriented motor skill training, impairment-appropriate difficulty, and performance feedback that motivates iterative play and skill improvement. Paddle Ball (i.e., Pong) is a simplified tennis simulation that uses hand movement to control a vertically moving paddle. Skee Ball uses hand-opening speed to launch balls at targets. Sound Tracker requires the

hand to precisely follow a moving track generated by different songs. Marble Maze uses hand opening to rotate mazes and guide marbles out into a bucket.

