### **Data analysis**

We will use a descriptive approach using means and standard errors to assess the effect of hand opening repetitions on the treatment group over time for each outcome. Due to the small sample size in our dataset, we will use a robust estimator to calculate the standard errors.

Upper extremity motor function will be assessed at enrollment, 6 weeks (end of treatment), and at 12 weeks post-treatment by a blinded assessor therapist. All assessments will be performed without any assistance from the stimulator and assessments will take place at least 24 hours after their last treatment session in order to avoid any transient carry-over effect or muscle fatigue. Change scores from the following outcomes will be calculated for each subject.

Descriptive statistics will be used to describe the results across patients and paired t-tests will be used to analyze the pre-post changes.

- Finger movement tracking error (squared sum distance from the target).
- Box and Block Test number of blocks successfully moved.
- Melbourne Assessment 2 percent score (0-100%).
- Assisting Hand Assessment score.

Additionally, adherence will be determined by downloading usage data from both the stimulator and the computer (via a portable USB thumb drive) – which will be used to calculate the percentage of prescribed treatment time completed by each participant. Participants will also be asked at every visit to report any difficulties or complications they may have experienced during home treatment sessions. Then, at the end of treatment, every participant will be interviewed regarding their impression of treatment and dosage, how easy or difficulty it was to use the equipment and play the games, and what changes they would suggest to the equipment or treatment dose, and whether or not they thought the treatment made any difference in their hand function. The number of hand opening repetitions will be recorded at each training session.

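### The pilot is meant to supply the effect for powering a larger trial, but 20 children fix it only to about ±0.94 SD, and no between-arm estimate, interval or rule for that uncertainty is planned

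*Combined protocol and SAP*

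**What the plan says.** - **Purpose.** Under Sample size determination, the trial "aims to estimate the intervention effect necessary to power a larger trial". The Rationale also makes estimating efficacy the purpose, and Specific Aims makes it the primary aim. Specific Aims shows that the effect meant is a between-arm one: "estimating its effect is a first step to test our hypothesis that it leads to greater outcomes than video game therapy alone".
- **Size.** "The sample size target of 20 participants was limited by the amount of funds provided by the R21 funding mechanism". No precision target, effect size, SD, alpha, power or dropout allowance accompanies this number.
- **Design.** "Twenty participants will be randomized to either a group treated with neuromuscular electrical stimulation and video games or video games alone". The allocation ratio is not stated. Methods and Procedures says only that "An adaptive randomization algorithm will be used to balance the two groups with respect to age, gender, and baseline severity".
- **Analysis.** Under Data analysis, "We will use a descriptive approach using means and standard errors", a sentence about hand-opening repetitions in the treatment group. For the four listed outcomes, "Change scores from the following outcomes will be calculated for each subject" and "paired t-tests will be used to analyze the pre-post changes". No between-arm difference or confidence interval is named, and neither the SD nor the baseline-to-follow-up correlation is listed as a result.
- **From pilot to trial.** No rule says how the estimate would become a sample size.

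**The concern.** An effect estimate from 20 children is a weak planning value. Required sample size varies with the inverse square of the effect, so a modest error in the estimate becomes a large error in the size of the next trial. A high estimate by chance gives a trial that is too small; a low one may lead to a useful treatment being dropped.

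A pilot this small can contribute other planning quantities more usefully: the SD of the outcome, its correlation with baseline, retention and adherence. Only adherence is explicitly planned.

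The problem is separate from the missing between-arm analysis. The precision computed below already assumes a correct between-arm comparison on one outcome. Adding that comparison would supply the estimate but would not make it precise.

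**Working it through.** **Inputs from the documents.** 20 children, two arms, change scores. The 20 comes from funding, so there is no calculation to reproduce.

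**Assumptions, because the documents give no figure.** 1:1 allocation (10 + 10); no dropout; two-sided 95% interval; no baseline adjustment; a larger trial with two-sided alpha 0.05 and 80% power; true effects from 0.2 to 1.0 SD. The SD unit is the between-child SD of the analysed score.

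**1. Precision.** Half-width = t(0.975, 18) × √(1/10 + 1/10) = 2.101 × 0.447 = **0.94 SD**.

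| Variation | Half-width |
|---|---|
| Split 9/11 to 7/13 | 0.94 to 0.98 SD |
| 9 completers per arm | 1.00 SD |
| 8 completers per arm | 1.07 SD |
| Baseline-adjusted, correlation 0.5 (assumed) | 0.82 outcome SD |
| Baseline-adjusted, correlation 0.7 (assumed) | 0.67 outcome SD |

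The adjusted rows use t(0.975, 17) = 2.110 and the factor √(1 − r²): 2.110 × 0.447 × 0.866 = 0.82, and 2.110 × 0.447 × 0.714 = 0.67. They are in SDs of the outcome itself, not of change. For scale, a half-width of 0.5 SD without adjustment would need 32 children per arm.

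**2. What one result would say.** An observed effect of 0.5 SD has an exact 95% interval of −0.40 to 1.38 SD. With n per arm = 2(1.960 + 0.842)²/d², the larger trial needs:

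- d = 0.2: 393 per arm
- d = 0.5: 63 per arm (64 with the usual addition of one for the t-test)
- d = 0.8: 25 per arm
- d = 1.44 (0.5 + 0.94): 8 per arm

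**3. Consequence of sizing on the point estimate.** Pilots of 10 + 10 were simulated (1,000,000 per true effect). The next trial was sized at 80% power on the observed effect, and its power was then evaluated at the true effect. Underpowered means true power below 80%.

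| True effect (SD) | Underpowered, given a positive estimate |
|---|---|
| 0.2 | 75% |
| 0.3 | 67% |
| 0.5 | 58% |
| 0.8 | 52% |
| 1.0 | 50% |

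With a small-sample bias correction to the estimate, these become 74, 66, 56, 49 and 46%. Over all pilots, including those with a zero or negative estimate (which lead to no trial), the underpowered share is about 50% at every true effect, because a nearly unbiased estimate overshoots about half the time.

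The wrong-sign share is 25% of pilots at a true 0.3 SD, 13% at 0.5 SD and 4% at 0.8 SD. At a true 0.5 SD, the planned size among positive pilots runs from about 13 to about 650 per arm (10th to 90th percentile), against 64 needed.

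**The case against.** The strongest reply is that this is an openly labelled pilot whose size was set by funds. It makes no precision claim, and it contains neither a rule that the raw estimate will be used unaltered nor a go/no-go rule. What happens in the larger trial is for a later protocol. All of that stands. Twenty children is not in itself an error, and the consequence in step 3 is conditional on a use of the estimate that the plan allows but does not prescribe.

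Part of the need is also already met. Adherence is planned as a percentage of prescribed treatment time, usage logs and an end-of-treatment questionnaire address feasibility, and a paired t-test on change requires the SD of change. Even so, nothing commits the authors to reporting that SD by arm, the baseline correlation or retention.

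A reader might infer that a trial sized on this pilot would be underpowered more often than not, without qualification. The calculations do not support that. The share exceeds one half only after conditioning on a positive estimate, and clearly so only for small to moderate true effects.

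A reader might also infer that sizing on a worthwhile difference cures low power. It does not. With a planning difference of 0.5 SD and the pilot SD inflated by 1.18, about 18% to 19% of trials fall below 80% power if the true effect is exactly 0.5 SD, but 67% do at 0.4 SD and 99% at 0.3 SD. The approach is defensible because effects below the stated difference are deliberately not targeted.

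**Conclusion.** The point holds in a conditional form. The purpose given for the pilot is to supply a planning effect, yet a between-arm difference from 10 + 10 children carries about ±0.94 SD, and the analysis section plans neither that difference nor its interval. The figure rests on equal allocation, full completion and no adjustment, in SDs of the analysed score.

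If the larger trial were sized on the point estimate and launched only after a positive one, 58% to 75% of such trials would be underpowered for true effects of 0.5 down to 0.2 SD. For 0.8 to 1.0 SD the share is about 50%. These are assumed effects, since the documents give none.

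The harm is downstream: nothing here biases the pilot or affects its participants. The plan should be changed, but this is not a defect that must stop the trial.

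**What to change.** **Sample size determination.** State the expected precision with its assumptions: allocation, number of completers and SD unit. Possible wording: *With 10 children per arm completing, an unadjusted between-arm difference will be estimated to within about ±0.94 SD of the analysed score (95% confidence interval), or about ±1.00 to ±1.07 SD with 9 or 8 completers per arm. The point estimate will not by itself serve as the planning effect. The larger trial will be sized on a minimum worthwhile difference stated and justified in advance, using a conservative upper limit for the pilot SD.*

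One such limit is the one-sided 80% upper confidence limit, which multiplies the SD by √(18/χ²(0.20, 18)) = 1.18.

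**Data analysis.** For each outcome and post-baseline visit, report the between-arm difference with its 95% confidence interval, the pooled within-arm SD and the baseline-to-follow-up correlation. Add retention by arm. Adherence is already covered.

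**Cost.** Two paragraphs of wording, with no new data or patients. The pilot gives up the claim to deliver the planning effect, and the sponsor must justify a worthwhile difference, which the documents do not supply.

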### **Data analysis**

We will use a descriptive approach using means and standard errors to assess the effect of hand opening repetitions on the treatment group over time for each outcome. Due to the small sample size in our dataset, we will use a robust estimator to calculate the standard errors.

Upper extremity motor function will be assessed at enrollment, 6 weeks (end of treatment), and at 12 weeks post-treatment by a blinded assessor therapist. All assessments will be performed without any assistance from the stimulator and assessments will take place at least 24 hours after their last treatment session in order to avoid any transient carry-over effect or muscle fatigue. Change scores from the following outcomes will be calculated for each subject.

Descriptive statistics will be used to describe the results across patients and paired t-tests will be used to analyze the pre-post changes.

- Finger movement tracking error (squared sum distance from the target).
- Box and Block Test number of blocks successfully moved.
- Melbourne Assessment 2 percent score (0-100%).
- Assisting Hand Assessment score.

Additionally, adherence will be determined by downloading usage data from both the stimulator and the computer (via a portable USB thumb drive) – which will be used to calculate the percentage of prescribed treatment time completed by each participant. Participants will also be asked at every visit to report any difficulties or complications they may have experienced during home treatment sessions. Then, at the end of treatment, every participant will be interviewed regarding their impression of treatment and dosage, how easy or difficulty it was to use the equipment and play the games, and what changes they would suggest to the equipment or treatment dose, and whether or not they thought the treatment made any difference in their hand function. The number of hand opening repetitions will be recorded at each training session.

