- i. Rehabilitation clinic sessions – These will occur up to twice per week for the first 3 weeks and once per week for the second 3 weeks of the 6 week treatment. They are therapist-guided and last up to 90 min consisting of 45 minutes of CCFES-mediated video games and up to 45 minutes of CCFES-mediated functional task practice. Early sessions will focus on training the patient and caregiver to self-administer play of a CCFES-mediated video game at home. As proficiency with one game develops, more games will be introduced. The functional task practice part of the session will engage the participant in using the CCFES system to assist them in practicing using their hand in activities such as lacing beads, throwing balls, eating finger foods, and other play and activities of daily living.
- ii. Home sessions – These consist of CCFES-mediated hand opening and video game exercises with caregiver assistance and supervision as needed. As proficiency develops and more games are added, each home session will increase in duration up to 90 minutes per day, as determined by the treating therapist based on the adherence of each participant. Self report of game difficulty and engagement will be made at the completion of each game (see below)

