- Assisting Hand Assessment examines the ability of a child to use both hands during play tasks (such as wearing a hat, bang cymbals together, hold a bottle with one arm and manipulate marbles with the other, etc.) This test has two components, a score and a description of hand function. The score reflects how well the impaired hand assists the other and ranges from 22 points (if the impaired hand is not used at all) to 88 points (if the affected hand is used like a normal non-dominant hand). The descriptions detail whether the child grasps an object from the table or from the other hand, how stable objects are in the hand, and how quickly use of the affected hand is initiated relative to the other hand. This test takes 15-20 minutes to administer.
- Number of Hand Opening Repetitions will be counted during task practice and during video game play. During video game play, repetitions are detected by a change in the sign of the first difference (analogous to finger velocity) of the bend sensor signal. We will use the total number of repetitions for correlations.

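### The repetition analysis is an unadjusted, non-randomised association that the plan calls an effect, and the arms it covers are not stated

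*Combined protocol and SAP*

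**What the plan says.** The Data analysis section opens with a descriptive approach "to assess the effect of hand opening repetitions on the treatment group over time for each outcome" and adds that, because the sample is small, "we will use a robust estimator to calculate the standard errors". The type of estimator is not named. For the outcome scores, the same section says "paired t-tests will be used to analyze the pre-post changes". No covariate appears in any analysis.

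Under Outcome Measures, repetitions are counted in task practice and in video game play. In the games, "repetitions are detected by a change in the sign of the first difference (analogous to finger velocity) of the bend sensor signal". That section ends: "We will use the total number of repetitions for correlations". It does not limit this to one arm. The Data analysis section adds: "The number of hand opening repetitions will be recorded at each training session".

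Methods and Procedures states that "The treatment dose will be the same for both groups". It also says that home sessions lengthen over time, "as determined by the treating therapist based on the adherence of each participant". Baseline MACS severity is a balancing factor in the randomisation and is not used afterwards.

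**The concern.** Randomisation protects the comparison of the two arms. It does not protect a comparison of children who completed many repetitions with children who completed few. If adherence, motivation or initial hand ability influences both the count and the improvement, the two will be associated even when repetitions do nothing.

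The plan calls this relation an effect and adjusts for nothing. The pilot is meant to inform a larger trial, so an association read as dose-response could feed into the choice of treatment dose there. The group wording adds a second problem: two analysts could apply the same sentence to different sets of children.

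**Working it through.** **The plan's own figures.** The plan gives no correlation, effect size or standard deviation for this analysis, and its total of 20 is set by funding, so there is no derivation to reproduce. The stated dose can be checked. It comprises 10 × 6 = 60 home sessions and 2 × 3 + 1 × 3 = 9 clinic sessions. At the 90-minute maximum, the clinic sessions take 13.5 h, which leaves 58 − 13.5 = 44.5 h, or about 45 minutes per home session. The planned dose is therefore common to all children. Differences in repetitions between children come from what is actually delivered and performed.

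**Is the exposure assigned?** Set side by side:
- Repetitions are recorded at training sessions, so they arise after randomisation.
- Home duration is set by the therapist from adherence. The documents state this pathway directly.
- Game repetitions are read from finger movement on the paretic hand, so hand ability plausibly affects the count. The documents do not show this.
- Severity and baseline scores are collected but are not used in this analysis.

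**How large could the bias be?** Assume a single confounder with correlation ρ to both repetitions and change score, and no true repetition effect. The expected spurious correlation is ρ × ρ = ρ². For ρ = 0.6 it is 0.36. All ρ values are assumptions. The table gives simulation results (10,000 replicates per setting, two-sided 5% test of the correlation). The n = 10 column represents one arm under an assumed 1:1 split, because no ratio is stated.

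| ρ | ρ² | mean r, n = 10 | rejection, n = 10 | rejection, n = 20 |
|---|---|---|---|---|
| 0 | 0 | 0.00 | 5% | 5% |
| 0.3 | 0.09 | 0.08 | 5% | 6.5% |
| 0.5 | 0.25 | 0.24 | 11% | 19% |
| 0.6 | 0.36 | 0.35 | 17% | 35% |
| 0.7 | 0.49 | 0.47 | 32% | 62% |

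With adjustment for the confounder (partial correlation), mean r is about 0 and rejection is 4.5% to 5.3% in every setting. That is a best case, because the simulation adjusts for the confounder itself, measured without error. If the confounder acts in opposite directions on repetitions and gain, the expected correlation is −ρ² and the two-sided rejection rates are the same by symmetry.

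Pooling the arms without adjustment makes false rejection more frequent (17% becomes 35% at ρ = 0.6), because a larger sample detects the spurious correlation more reliably.

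**Precision.** The Fisher interval is tanh(atanh r ± 1.96/√(n − 3)). For r = 0.36 it is −0.35 to 0.81 at n = 10 and −0.10 to 0.69 at n = 20. A two-sided p < 0.05 needs |r| above 0.63 and 0.44 respectively.

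**Do robust standard errors help?** No. They concern the variance, not confounding. In one assumed form (HC0 with a normal critical value), rejection with no confounding at all is 18% at n = 10 and 11.5% at n = 20. The plan names no form, so this is only an example.

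**The case against.** The strongest reply is that the plan calls the approach descriptive and attaches no test or model to repetitions, and that elsewhere it uses the neutral word correlations. This stands in part. It means the rejection rates above illustrate what happens if a test is applied and are not a property of a planned test. It does not remove the word effect or supply any adjustment.

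The bias is also assumed. The documents give no correlation between severity and either repetitions or gain, and they do not fix the sign: more severely affected children may have more room to improve. At ρ = 0.3 the inflation is negligible. All of this stands.

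A reader might infer more than the documents support:
- *That this is the lead analysis.* It is merely listed first. No primary analysis is named.
- *That control children are excluded and half the data discarded.* The phrase about the treatment group is loose. The correlations are not restricted by arm, and both arms receive the same practice and games. The supportable point is that coverage is unclear.
- *That the trial asks whether stimulation adds anything beyond extra repetitions.* The Rationale, Specific Aims and sample size sections ask whether stimulation plus games improves on games alone. The former is a mediation question that the documents do not pose.
- *That a model with arm and repetitions would separate the two.* It conditions on a post-randomisation variable and leaves motivation and adherence unadjusted. Stimulation-arm repetitions may also be assisted, so a repetition need not be the same exposure in each arm. This is a fair argument for displaying the arms separately.

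The Data analysis section also writes out no between-arm comparison. That is a separate gap and is not counted here.

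**Conclusion.** The point holds in limited form. As written, the plan would yield a confounded association under the name of an effect, in a set of children that is not clearly defined. This rests on the text alone: repetitions are not assigned, home duration follows adherence, and nothing is adjusted for.

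The magnitude does not rest on the text. The range of 5% to 32% false rejection at n = 10 depends on a single confounder, assumed correlations of 0.3 to 0.7, an assumed 10 children per arm and an added significance test. No single value in that range, nor the direction of bias, should be cited as what this trial would show. The point concerns interpretation of a supporting analysis. The data remain usable.

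**What to change.** In the Data analysis section:
1. Replace *effect of* with *association with*, and label the repetition analysis exploratory and secondary to the randomised between-arm comparison.
2. State that it covers both arms, with results shown by arm because stimulation-arm repetitions may be assisted.
3. Adjust for baseline score and MACS severity, and report estimates with 95% confidence intervals.
4. State that an arm coefficient conditioned on repetitions will not be interpreted as the effect of stimulation beyond repetitions.
5. State that confounding by motivation and adherence remains after adjustment.

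MACS level, baseline scores and repetition counts are already collected, so the change costs wording and one model. The statistical cost is degrees of freedom. With MACS severity in the two levels used at randomisation, a pooled model with intercept, arm, baseline score, severity and repetitions leaves 20 − 5 = 15 residual degrees of freedom. A model within one arm, without the arm term, leaves 10 − 4 = 6 under the assumed equal split. Intervals will be wide and should be reported as such.
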